8.5 Benefit/risk analysis

Benefits

Tapentadol has been shown to be effective for the treatment of moderate to severe pain in adults (Section 6.2). Although data on the specific efficacy of opioids in children and adolescents is limited, it is not expected that these will deviate notably from those observed in adults. A single dose pharmacokinetic trial [REDACTED] in the same age group as the population in this trial has been recently performed by the sponsor, the data of which confirmed the dosing of tapentadol PR used in this trial.

The comparator in this trial, morphine PR, is a well-known opioid analgesic with proven efficacy in adults.

In addition, subjects enrolled in this trial will be intensively monitored during the treatment period, more closely than in routine clinical practice.

Risks

Lack of efficacy

Tapentadol may not be as efficacious in children and adolescents as it is in adults, even if the exposure is comparable. However, this is considered to be unlikely.

During the Treatment Period, rescue medication, in the form of morphine oral solution, will be available for use as rescue medication if pain relief is insufficient. Thereafter, subjects may receive immediate release strong opioids for treatment of breakthrough pain and incidental pain.

Safety

The potential risks to subjects in this trial include exposure to tapentadol and morphine, with a potential for side effects. Since most of these side effects are related to the use of opioids, i.e., class related, and the subjects would anyway require opioid treatment, the added safety risk is considered acceptable.

Data on the specific risks of opioids in children and adolescents is limited. However, it is not expected that the specific risks of opioids in children and adolescents will deviate from those observed in adults.

Subjects will be monitored for adverse events throughout the trial, and experts in pediatric pain will conduct the trial.

Safety – tapentadol

The assessment of risk for the tapentadol PR is mainly based on experience in adults with the solid oral formulations tapentadol IR and tapentadol PR (and a related tamper resistant formulation).

Confidential

Protocol KF5503-66
including Amendment 05Page 46 of 137
DMS version 9.0
27 Jul 2017

The safety profile of tapentadol has been well characterized through a completed clinical program in adults and post-marketing experience is now available. The safety of tapentadol PR has been demonstrated in a 1 year safety trial in adults.

The potential risks to subjects in this trial include long-term exposure to tapentadol PR, with a potential for side effects not discovered during single dose treatment in children and long-term treatment in adults. However, it is not expected that the safety profile of tapentadol will deviate notably from that in adults based on the pharmacodynamic and pharmacokinetic properties of tapentadol.

Safety – general and blood sampling

This trial has been designed to protect the interests of the subjects, minimizing the risk to them, and ensuring compliance with recommendations (EMEA ad hoc working party 2008) for the amount of blood drawn (see Section 12.1). Blood sampling for pharmacokinetic assessments and safety monitoring will be performed. These are the only invasive procedures associated with the trial. Risks to subjects include stress and discomfort, and the risks associated with the blood sampling process (venipuncture) and the volume of blood drawn.

To reduce the subject stress and discomfort, only staff with experience working with children or adolescents will draw blood and the application of a local anesthetic before venipuncture is recommended. Also, no more than 2 attempts to collect blood for pharmacokinetic evaluations will be done at any visit.

To keep the volume of blood drawn to a minimum, only laboratories will be used with expertise in handling and analyzing biological samples using small volumes. The number of venipunctures will also be kept to a minimum.

Data monitoring committee

To allow early signal detection and to ensure the safety of the trial subjects, an independent DMC (see Section 5.4) will be established to oversee and evaluate data from selected pediatric trials with tapentadol administration performed by Grünenthal. The DMC will review and evaluate the data provided, as defined in a DMC charter, on an ongoing basis. The DMC will provide recommendations to the sponsor's steering committee as described in the DMC Charter.

Conclusion

The efficacy of tapentadol is expected to be similar in children and adolescents to that seen in adults. The risks associated with the trial, and the risks associated with the administration of tapentadol and morphine, are adequately addressed by the mitigation procedures. As the trial generates data that will support the prescribing of tapentadol for control of pain in the pediatric population, the overall risk-benefit assessment is considered to be such that the trial can be ethically performed.

9 SUBJECT ENROLLMENT AND TRIAL DISCONTINUATION

9.1 Subject enrollment procedure

Before the informed consent form and, if applicable, the assent form, is signed, the subjects will be screened to identify subjects who could potentially be enrolled into the trial.

Confidential

Protocol KF5503-66
including Amendment 05Page 47 of 137
DMS version 9.0
27 Jul 2017

If a subject is identified to be potentially eligible, the subject, parent(s), or legal guardian(s) will be requested by the investigator to give consent/(if applicable) assent for the subject's enrollment in the trial as described in Section 4.2.

The investigator will keep a subject screening log and a subject identification and enrollment log.

9.2 Inclusion/exclusion criteria

9.2.1 Inclusion criteria

See Section 1.3.1.

9.2.2 Exclusion criteria

See Section 1.3.2.

9.2.3 Inclusion criteria for the Tapentadol Period (Part 2)

See Section 1.3.3.

9.2.4 Criteria for entry into the Tapentadol Period or Observation Period

Subjects completing the Treatment Period (Part 1) with tapentadol PR or morphine PR and who have need for continued opioid treatment can enter the Tapentadol Period (see Section 1.2.2).

Subjects not completing the Treatment Period (Part 1), but who have taken at least 1 dose of IMP, and those who complete the Treatment Period, but who do not want to continue with tapentadol PR treatment, will enter the Observation Period (12 months) (see Section 1.2.3).

9.3 Trial discontinuation and treatment not completed

Subjects may stop taking IMP (treatment not completed) during the trial, but continue in the Observation Period. Subjects may, however, also discontinue participation in the trial completely (trial not completed).

9.3.1 Reasons for discontinuation of a subject from IMP (treatment not completed)

The investigator must discontinue subjects from treatment with IMP (i.e., treatment not completed) for the compulsory reasons (stopping criteria) given in Table 1. For reasons marked as optional, the investigator may decide to stop IMP administration if the benefit/risk ratio for continued administration of IMP is considered not to be favorable.

Table 1: Reasons for compulsory and optional discontinuation of subjects from investigational medicinal product (treatment not completed)

Main reason	Discontinuation from IMP	
	Compulsory	Optional
Adverse event		X
- There is any relevant deterioration in the health of the subject that could alter the benefit/risk assessment for the subject, including adverse events, laboratory parameters, vital signs, or other safety parameters (e.g., ECG).		

Confidential

Protocol KF5503-66
including Amendment 05

Page 48 of 137
DMS version 9.0
27 Jul 2017

Main reason	Discontinuation from IMP	
	Compulsory	Optional

 - A confirmed QT or QTc interval of >470 ms. - Based on data from the central laboratory, clinically relevant change in liver parameters after dosing if the result is confirmed by 1 additional laboratory assessment (see Section 19.7), for 1 or more of: 
 • Alanine transaminase or aspartate transaminase is >5 times above the upper limit of normal. • Alanine transaminase or aspartate transaminase is >3 times above upper limit of normal and total serum bilirubin >2 times above upper limit of normal or international normalized ratio (INR) >1.5 times above the upper limit of normal (without documented pathological screening value or without pharmacological anticoagulation with vitamin K antagonists). 	X	
Death (trial discontinuation)		X
Lack of efficacy		

 - The subject requires more than 4 doses per day of rescue medication on 2 consecutive days for persistent intolerable pain while taking the highest dose of IMP twice daily. 	X	
Pregnancy	X	
Enrollment failure (trial discontinuation)	X	
Protocol deviation		

 - The subject is non-compliant with requirements of the trial. - Subject is using drugs or medical devices that have no marketing authorization for human use. - The subject continues to take more than the maximum allowed dose of IMP after being reminded not to do so. - Subject continues to take less than the minimum allowed dose of IMP according to weight group (see Table 2 and Table 3) after being reminded not to do so. 		X

 - A female subject becomes post-menarchal or turns 12 years of age and is not abstinent, or, if sexually active, is not practicing an effective method of birth control (e.g., prescription oral contraceptives, contraceptive injections, intrauterine device, double-barrier method, contraceptive patch). - The subject is taking forbidden medication (see Section 10.5.2). - Surgery during Part 1 (Treatment Period) of the trial that requires post-surgical ICU treatment, or that requires post-surgical parenteral pain-treatment, or, in the opinion of the investigator, affects the safety of the subject. 	X	
Lost to follow-up (trial discontinuation)	X	
Technical reasons		

 - Technical or logistical grounds (e.g., important technical equipment fails). - Subject no longer requires opioid analgesia. - Subject requires a change of route of analgesic administration, e.g., because they can no longer swallow the tablets. 		X
Withdrawal of informed consent (trial discontinuation)	X	
Trial terminated by the sponsor (trial discontinuation)	X	

Confidential

Protocol KF5503-66
including Amendment 05

Page 49 of 137
DMS version 9.0
27 Jul 2017

ECG = electrocardiogram; ICU = intensive care unit; IMP = investigational medicinal product.

9.3.2 Reasons for discontinuation of a subject from the trial

Following discontinuation of a subject from IMP, in certain cases (e.g., withdrawal of consent), the subject may also need to be discontinued from trial participation (see items marked trial discontinuation in [Table 1](#)).

9.3.3 Procedure for the handling of prematurely discontinued subjects

The investigator must inform the sponsor in writing about any discontinuation of a subject from the trial or from IMP (treatment not completed) and must document any such discontinuation of a subject. The investigator must update the interactive response technology system and CRF within 48 hours of a subject discontinuing. In case of death or any other serious adverse event, the sponsor or the sponsor's authorized delegate must be informed according to the requirements defined in the corresponding protocol section about notification of serious adverse events. Where applicable, the relevant IEC or IRB must be informed with a detailed written explanation. Also, any technical devices provided to the subjects, e.g., electronic diaries, must be collected.

For all subjects discontinuing the trial or discontinuing IMP (treatment not completed; these subjects may continue the trial in the Observation Period), the following information must be documented:

- Reason for discontinuation.
- If the parent/legal guardian/subject agrees, perform all assessments for Visit VE or Visit ET as appropriate, and Visit F7D ([Section 1.2](#)).

For subjects discontinued from the trial, the following information must be documented:

- Status of all new and ongoing (serious) adverse events.
- All data captured until discontinuation as required at all attended visits, including the recording of concomitant medication taken until the day of discontinuation from the trial.
- Ensure the return of partially used and unused medication kits.
- Perform a final IMP and, if applicable, rescue drug accountability.
- Collect the diary and any other devices provided to the subject.
- If the subject agrees, perform all assessments/visits as given in [Section 1.2](#).

For subjects discontinued from IMP (treatment not completed), all efforts should be made to:

- Ensure the return of partially used and unused medication kits.
- Perform a final IMP and, if applicable, rescue drug accountability.
- Collect the diary and any other devices provided to the subject.
- If the subject agrees, perform all assessments/visits as given in [Section 1.2](#).

Subjects turning 18 years old before Visit VE may continue in the trial. However, an additional subject will then be enrolled and allocated to IMP. Otherwise treated subjects will not be replaced. See [Section 3](#) for a definition of allocated and treated subjects. Replacement subjects will receive

Confidential

Protocol KF5503-66
including Amendment 05

Page 50 of 137
DMS version 9.0
27 Jul 2017

the same sequence of treatments and undergo the same procedures and assessments up to Visit VE as the initially entered subjects.

9.3.4 Premature termination or suspension of the trial

The relevant IEC or IRB, the regulatory authorities, or the sponsor or the sponsor's authorized delegate alone or in conjunction have the power to make a binding decision to prematurely terminate or suspend the trial at any or all trial sites. In addition, for an individual trial site, this decision can be made by the principal investigator.

The party prematurely terminating or suspending the trial must promptly inform all other parties (i.e., the principal investigator(s), the relevant IEC or IRB, the regulatory authorities, or the sponsor/the sponsor's authorized delegate, as applicable).

In addition, the investigator must promptly inform the subjects, ensure appropriate follow-up for any enrolled subjects, and provide the relevant IEC or IRB and the sponsor or the sponsor's authorized delegate, as applicable, with a detailed written explanation of the termination or suspension.

The international coordinating investigator has to be informed immediately if the trial is prematurely terminated or suspended.

10 TREATMENTS

10.1 Investigational medicinal product

10.1.1 Identity and composition – tapentadol PR (test)

Name: Tapentadol prolonged release tablets

Substance code: CG5503

Substance name: Tapentadol hydrochloride

Active component(s): Tapentadol

Dose (strength): 25 mg, 100 mg tablets (tapentadol)

Manufacturer: Grünenthal GmbH, Aachen, Germany

For further information about the identity and composition of tapentadol PR, see the current investigator's brochure and the clinical supply specification.

10.1.2 Identity and composition – morphine PR (comparator)

Name: Morphine prolonged release tablets

Substance name: Morphine sulfate

Active component(s): Morphine

Dose (strength): 10 mg, 30 mg tablets (morphine sulfate)

Final release of the re-packaged product: Grünenthal GmbH, Aachen, Germany

10.1.3 Packaging and labeling

The IMPs will be manufactured as single oral dosage forms and packed in blister packs. For detailed information about the packaging and labeling, see the clinical supply specification.

10.1.4 Delivery, storage and disposal

The sponsor is responsible for supplying the investigator with IMP. These will not be delivered until all required documentation (EC/IRB approval, authority approval, signed contract and protocol, curriculum vitae) is present at the sponsor.

Storage conditions will be specified on the labels of the IMPs.

For countries in which tapentadol and morphine have been classified as a controlled/scheduled substance, all local requirements for handling, storage, and distribution of narcotics will be followed. Controls will be implemented at the trial site to ensure documented compliance with these requirements.

10.2 Administration of trial treatments

10.2.1 Administration

The route of administration is oral. Tablets should be taken with at least 50 mL of water or other suitable fluid. Tablets can be taken irrespective of food intake.

Subjects taking tapentadol PR 100 mg or more can decide if they prefer to take the smaller tapentadol PR 25 mg tablets or a combination of tapentadol PR 25 mg and tapentadol 100 mg tablets.

The time of IMP administration and the number of tablets per dose will be captured in the diary during Part 1 (Treatment Period).

All restrictions and precautions listed in the investigator's brochure for tapentadol PR and in the summary of product characteristics for morphine PR must be followed.

The first dose of IMP will be taken during Visit V2 (Allocation Visit).

A dose must not be repeated if a subject vomits or regurgitates part or all of a dose. Vomiting and/or regurgitation of a dose must be recorded as an adverse event.

10.2.2 Total number of doses and dosing interval

The IMP will be taken for 14 (± 1) days in Part 1 (Treatment Period) and, thereafter (tapentadol PR only), for up to \sim 12 months in the Tapentadol Period of Part 2. Dosing will be twice daily with a dosing interval of \sim 12 hours (but not less than 6 hours).

10.2.3 Dose

10.2.3.1 Starting doses in Part 1 for subjects without previous opioid treatment

Subjects will start with the minimum dose (Dose level 1) of tapentadol PR ([Table 2](#)) or morphine PR ([Table 3](#)).

Confidential

Protocol KF5503-66
including Amendment 05

Page 52 of 137
DMS version 9.0
27 Jul 2017

10.2.3.2 Starting doses in Part 1 for subjects with previous opioid treatment

Subjects taking previous opioid treatment will start at 70% of the equi-analgesic dose of their previous treatment or lower; depending on the available dose, but using at least the minimum dose according to weight group (see [Table 2](#) for tapentadol PR and [Table 3](#) for morphine PR).

Subjects pre-treated with morphine can continue on their previous dose or next lower dose according to [Table 2](#) if the dose does not match a dose given on the dosing table, if randomized to morphine.

Conversion from other opioids to morphine should be done according to clinical routine. To calculate the dose of prolonged release opioids per intake, it is recommended to calculate the total daily dose of the immediate release opioid and divide the result by 2. To rotate subjects from other opioids to tapentadol PR, the morphine-equivalent dose should be calculated first followed by the calculation of the final tapentadol PR dose (1 mg morphine PR is equivalent to 2.5 mg tapentadol PR).

10.2.3.3 Starting dose of tapentadol PR in Part 2

Subjects converting from morphine PR (Treatment Period of Part 1) to tapentadol PR (Tapentadol Period of Part 2) will start tapentadol PR at 70% of the current morphine equivalent dose or lower, depending on the available dose, but using at least the minimum dose according to their weight group ([Table 2](#)).

Subjects treated with tapentadol PR during Part 1 (Treatment Period) will continue on the last dose taken during Part 1 and the dose can be adjusted within the pre-defined limits as required during Part 2.

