1.3 Inclusion/exclusion criteria

1.3.1 Inclusion criteria

Subjects are eligible for the trial at Visit V1 if all the following apply:

Inclusion criteria	Rationale for criterion
1. Informed consent/(if applicable) assent obtained.	Legal requirement.
2. Male or female subject at least 6 years of age at the Enrollment Visit and less than 18 years of age on the predicted day of Visit VE.	Standardization of trial population.
3. Subject has an underlying long-term pain condition (e.g., cancer, chronic disease, planned or performed surgery) that is, according to the judgment of the investigator, expected to require a twice-daily prolonged release opioid treatment until at least the end of the 14-day Treatment Period (Visit VE).	Standardization of trial population.
4. Subject can swallow tablets of appropriate size.	Logistical requirement.
5. Subject is able to participate in the trial as planned and willing to comply with the requirements of the protocol including refraining from drinking beverages containing alcohol and recreational intake of drugs while on IMP.	Safety, standardization of trial population, and practical consideration.

Subjects must satisfy the following criteria at Visit V2 to be allocated to IMP:

Inclusion criteria	Rationale for criterion
6. Less than 18 years of age on the planned day of Visit VE.	Standardization of trial population.
7. No opioid intake or last calculated morphine equivalent dose at day of allocation of <3.5 mg/kg per day.	Standardization of trial population.
8. Subject has a body weight of ≥ 17.5 kg.	Standardization of trial population.
9. If a female of childbearing potential (post-menarchal and not surgically incapable of childbearing) and sexually active, must practice an effective method of birth control (e.g., prescription oral contraceptives, contraceptive injections, intrauterine device, double-barrier method, contraceptive patch) before allocation to IMP until the end of intake of IMP.	Safety.
10. If a female and post-menarchal or older than 12 years, has a negative urine pregnancy test on the day before or on the day of allocation to IMP.	Safety.

Note: Subjects will only receive IMP if documentation is available showing that they comply with all inclusion criteria.

Confidential

Protocol KF5503-66
including Amendment 05

Page 20 of 137
DMS version 9.0
27 Jul 2017

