10.2.4 Titration and dosing tables

Table 2: Tapentadol PR dosing table

Weight (kg)	Minimum/Starting dose ^a Dose level 1		Titration						Maximum dose Dose level 5	
			Dose level 2		Dose level 3		Dose level 4			
	M (mg)	E (mg)	M (mg)	E (mg)	M (mg)	E (mg)	M (mg)	E (mg)	M (mg)	E (mg)
17.5 to <22.5	25	25	50	50	-	-	-	-	75	75
22.5 to <27.5	25	25	50	50	75	75	-	-	100	100
27.5 to <32.5	25 ^b	50 ^b	75	75	100	100	-	-	125	125
32.5 to <40.0	50	50	75	75	100	100	125	125	150	150
40.0 to <45.0	50	50	100	100	125	125	150	150	175	175
45.0 to <50.0	75	75	100	100	150	150	175	175	200	200
50.0 to <55.0	75	75	100	100	150	150	200	200	225	225
55.0 to <60.0 ^c	75	75	100	100	150	150	200	200	250	250
≥60.0 ^c	100	100	125	125	150	150	200	200	250	250

a) Subjects taking less than the minimum dose according to their weight group may be discontinued from investigational medicinal product.

b) The first intake is 25 mg (irrespective whether first taken in the morning or evening) and the second and subsequent intakes are 50 mg.

c) Subjects with a bodyweight of 55.0 kg or higher will receive a maximum dose of tapentadol PR 250 mg twice daily.
 M = morning; E = evening; PR = prolonged release.

Table 3: Morphine PR dosing table

Weight (kg)	Minimum/Starting dose ^a		Titration								Maximum dose Dose level 5	
	Dose level 1		Dose level 2		Dose level 3		Dose level 4					
	M (mg)	E (mg)	M (mg)	E (mg)	M (mg)	E (mg)	M (mg)	E (mg)	M (mg)	E (mg)	M (mg)	E (mg)
17.5 to <22.5	10	10	20	20	-	-	-	-	30	30		
22.5 to <27.5	10	10	20	20	30	30			40	40		
27.5 to <32.5	10 ^b	20 ^b	30	30	40	40	-	-	50	50		
32.5 to <40.0	20	20	30	30	40	40	50	50	60	60	60	60
40.0 to <45.0	20	20	40	40	50	50	60	60	70	70	70	70
45.0 to <50.0	30	30	40	40	60	60	70	70	80	80	80	80
50.0 to <55.0	30	30	40	40	60	60	80	80	90	90	90	90
55.0 to <60.0 ^c	30	30	40	40	60	60	80	80	100	100		
≥60.0 ^c	40	40	50	50	60	60	80	80	100	100		

a) Subjects taking less than the minimum dose according to their weight group may be discontinued from investigational medicinal product.

b) The first intake (irrespective whether first taken in the morning or evening) is 10 mg and the second and subsequent intakes are 20 mg.

c) Subjects with a bodyweight of 55 kg or higher will receive a maximum dose of morphine PR 100 mg twice daily.

M = morning; E = evening; PR = prolonged release.

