10.6.2 Reasons for administration

Rescue medication may be given in Part 1 for:

- Breakthrough pain without clear cause.
- End-of-dose failure indicating a requirement of adjustment of the dose of IMP.
- Increased activity or movement (incidental pain).
- Withdrawal symptoms such as hyperalgesia that appeared during the first days of titration after the previous treatment with an opioid were stopped.
- Prevention of pain during titration, if considered necessary by the investigator.

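### The starting-dose rule for morphine-pretreated children randomised to morphine cites Table 2 (tapentadol PR) where Table 3 (morphine PR) is meant

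*Protocol*

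**What the plan says.** Protocol 10.2.3.2 sets Part 1 starting doses for children already on opioids. Its first paragraph gives the general rule: "Subjects taking previous opioid treatment will start at 70% of the equi-analgesic dose of their previous treatment or lower", with a floor at the weight-group minimum, taken from Table 2 for tapentadol PR and Table 3 for morphine PR.

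The second paragraph makes an exception for morphine: "Subjects pre-treated with morphine can continue on their previous dose or next lower dose according to". The table that it names at this point is Table 2. Two conditions limit the exception: "if the dose does not match a dose given on the dosing table, if randomized to morphine".

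Protocol 10.2.4 identifies the tables by their titles: "Table 2: Tapentadol PR dosing table" and "Table 3: Morphine PR dosing table". Footnote c to Table 3 adds a ceiling: "Subjects with a bodyweight of 55 kg or higher will receive a maximum dose of morphine PR 100 mg twice daily".

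**The concern.** The exception applies only to the morphine arm, yet it sends the prescriber to the other drug's dosing table. The two tables are on different milligram scales, so the error is not harmless in form. A prescriber who follows the sentence as printed may find no dose at or below the child's previous one, a dose that the morphine tablets cannot make up, or, in a heavy adolescent on a high previous dose, a figure above the protocol's own morphine maximum.

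What is at stake is the clarity and safety of an opioid starting dose in children. It is not a question of trial inference.

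**Working it through.** The plan gives no figure to reproduce here. The check compares the references and then looks at what each table would return.

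**Inputs**
- Doses per intake by weight band: Tables 2 and 3, Protocol 10.2.4. In the 27.5 to <32.5 kg band the maintained doses of 50 mg and 20 mg are used, not the reduced first intake.
- Morphine PR tablets of 10 mg and 30 mg: Protocol 10.1.2. With whole tablets, a makeable dose is a multiple of 10 mg.
- Limit on previous opioid: "last calculated morphine equivalent dose at day of allocation of <3.5 mg/kg per day" (Protocol 1.3.1, criterion 7). Per intake this is 3.5 / 2 = 1.75 mg/kg.

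**1. References side by side.** The Synopsis (Trial treatments), 10.2.3.1, the first paragraph of 10.2.3.2 and 10.2.3.4 all pair Table 2 with tapentadol PR and Table 3 with morphine PR. Section 10.2.3.3 uses Table 2 for tapentadol only. The second paragraph of 10.2.3.2 alone uses Table 2 for morphine.

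**2. Scale.** Dividing each Table 2 dose by its Table 3 counterpart gives 2.5 in 41 of 41 cells. In the lightest band the ratios are 25/10, 50/20 and 75/30; in the heaviest they are 100/40, 125/50, 150/60, 200/80 and 250/100. This is the protocol's own conversion of 1 mg morphine PR to 2.5 mg tapentadol PR.

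**3. Makeable doses.** Table 2 entries that are not multiples of 10 mg:
- 25 and 75 in each of the two lightest bands: 4
- 75 and 125 in each of the next two bands: 4
- 125 and 175 at 40 to <45 kg: 2
- 75 and 175 at 45 to <50 kg: 2
- 75 and 225 at 50 to <55 kg: 2
- 75 at 55 to <60 kg: 1
- 125 at 60 kg or more: 1

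The total is 4 + 4 + 2 + 2 + 2 + 1 + 1 = 16 of 41.

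**4. Illustrative lookups.** Weights and previous doses are assumed. Each previous dose is below 1.75 × weight. The entry is the highest table dose at or below the previous dose.

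| Weight | Limit per intake | Previous dose | Table 2 gives | Table 3 gives |
|---|---|---|---|---|
| 20 kg | 35 mg | 25 mg | 25 mg, not makeable | 20 mg |
| 30 kg | 52.5 mg | 45 mg | none (lowest 50 mg) | 40 mg |
| 47.5 kg | 83.1 mg | 65 mg | none (lowest 75 mg) | 60 mg |
| 70 kg | 122.5 mg | 95 mg | none (lowest 100 mg) | 80 mg |
| 80 kg | 140 mg | 130 mg | 125 mg, not makeable | 100 mg |
| 90 kg | 157.5 mg | 150 mg | 150 mg | 100 mg |

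**5. Conflict with the morphine maximum.** At 60 kg or more, Table 2 lists 125, 150, 200 and 250 mg, all above the 100 mg cap. An eligible child can have a previous dose of D mg per intake only if weight exceeds D / 1.75:
- 125 / 1.75 = 71.4 kg, but 125 mg cannot be made from the tablets.
- 150 / 1.75 = 85.7 kg, with a previous daily dose of at least 2 × 150 = 300 mg. This is the first makeable dose above the cap.
- 200 / 1.75 = 114.3 kg.

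**The case against.** The strongest reply is that nobody would be misled. The sentence itself limits the rule to the morphine arm, the sentence before it names Table 3 for morphine, each table is titled by drug, and Table 3 prints the 100 mg ceiling. The rule is permissive, and the next lower dose can never exceed what the child was already taking. Up-titration is possible after 2 days (10.2.3.4). Rescue morphine may be given for early withdrawal (10.6.2: "Withdrawal symptoms such as hyperalgesia that appeared during the first days of titration after the previous treatment with an opioid were stopped"). All of this stands, and it is why the point is minor.

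It is also fair to say that the frequency cannot be computed. The slip makes it unclear which table decides whether a previous dose is off-table: a prescriber who checks Table 3 for a match is already in the right place. The documents give no distribution of weights or previous doses. Any count of affected dose combinations would therefore measure an assumed reading rather than the trial.

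What does not stand is that the error can be left. It sits in the current text of an operative dosing instruction, and nothing in the documents supports using Table 2 for morphine.

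**Conclusion.** The cross-reference is wrong as written. Severity is minor. At most the morphine arm is exposed, 69 / 3 = 23 of the planned 69 children, and only those pretreated with morphine whose dose is off-table; how many that is cannot be known from the documents. The finding on makeable doses assumes whole tablets. The weights in the over-cap case follow from the eligibility limit split over two equal intakes.

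A reader might infer more than this, and the documents do not support it:
- **A 2.5-fold overdose.** The lookup returns a dose at or below the previous one, so the ratio between the tables does not carry over to the dose given. The over-cap case is remote and is contradicted by footnote c.
- **Systematic underdosing through the 70% rule.** No text says that a failed lookup sends the child there. If it did, the child would receive the protocol's general starting rule.
- **Bias in the responder comparison.** The SAP does not use this sentence, and nothing in the documents links it to responder status. The endpoint, alpha and sample size are unchanged.
- **Actual misdosing at sites.** The content of the interactive response system and the instruction sheets is not in the documents.

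**What to change.** In the second paragraph of Protocol 10.2.3.2, replace Table 2 with Table 3. Notify sites of the correction. Confirm that the interactive response system, which asks about previous opioid treatment for the first supply (Protocol 10.3.1), and the instruction sheets use Table 3 for morphine.

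With Table 3 cited, the six examples above give 20, 40, 60, 80, 100 and 100 mg, all makeable and none above the cap. The cost is a one-digit protocol correction, a site notice and a configuration check. There is no statistical cost.
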